1.0 Introduction

1.2 Overview and Study Rationale

Multiple myeloma constitutes approximately 10% of all hematologic malignancies. High-dose chemotherapy followed by autologous HCT remains an integral treatment strategy for multiple myeloma. Lenalidomide is the most commonly prescribed maintenance therapy after autologous HCT, however, disease relapse/progression after autologous HCT remains unavoidable secondary to the existence of minimal residual disease and drug resistance conferred by tumor microenvironment. When patients relapse/progress after autologous HCT, management of disease depends on prior treatment history, organ function and patient tolerability to certain chemotherapeutic agents. There are considerable practice variations in part due to several FDA approved antimyeloma agents and there is no consensus on how best to treat serologic relapse/progression without symptomatic disease after autologous HCT.

With the incorporation of free light chain assay into the standard clinical practice, relapse/progression of myeloma may be captured early and only limited literature is available to characterize the pattern of relapse/progression after autologous HCT. A Spanish group reported 4 distinctive patterns of relapse/progression including (1) extramedullary disease, (2) plasma cell leukemia, (3) clinically symptomatic disease (66%), and (4) insidious increase in serum M-spike (18%).⁵ More recently, Zamarin et al. evaluated 273 patients who underwent autologous HCT (79% of them not on maintenance) and showed that 85% of patient had asymptomatic relapse/progression detected by serologic testing whereas only 15% had symptomatic relapse/progression (characterized by anemia, renal failure, hypercalcemia, soft tissue or bone disease) after autologous HCT.⁶ The latter study demonstrated increasing frequency of serologic relapse without symptomatic disease after autologous HCT over time. It was also shown that the survival was better with asymptomatic relapse/progression.⁶ A Spanish group conducted an observation prospective registry study evaluating the timing and pattern of relapsed disease in myeloma patients.⁷ The median time from biological/serologic relapse to clinical (symptomatic) relapse was 105 days which is relatively short.⁷

Signaling Lymphocyte Activation Molecule family-7 (SLAMF7, also known as CS1 or CD319) is a human membrane glycoprotein and member of the immunoglobulin superfamily.^{8,9} SLAMF7 is expressed on myeloma cell surface on both primary human myeloma cells and myeloma cell lines.⁹ Soluble SLAMF7 has also been detected in myeloma patients' serum and has been shown to correlate with myeloma disease stage.⁸ Additionally, SLAMF7 is expressed in natural killer (NK) cells and T-cell subsets.^{10,11} The CS1/SLAMF7 gene is located on the long arm of chromosome 1 (1q23.1-1q24.1), and gains of chromosome 1q are relatively frequent in myeloma.¹² SLAMF7 has been demonstrated to co-localize with CD138 promoting cell-cell adhesion, and plays a role in myeloma cell interactions with bone marrow stromal cells.^{8,13} SLAMF7 is a self-ligand for NK cells and promotes activation through selective expression of the adaptor protein, EAT-2.¹⁴⁻¹⁶ Furthermore, SLAMF7 may inhibit T cells that lack EAT-2.¹⁴

Elotuzumab (previously called HuLuc63) is a humanized immunoglobulin G₁ anti-CS1/SLAMF7 monoclonal antibody that has been shown to impair myeloma cell adhesion. *In vitro* studies have shown impaired primary myeloma cell survival with or without bone marrow stromal cells.⁸ Elotuzumab is thought to exert effects on myeloma cells through antibody-dependent cellular cytotoxicity (ADCC) which is mediated by NK cells through interaction of their Fc_γ RIIIA receptor.^{8,9,17} Elotuzumab also directly activates NK cells through direct SLAMF7 ligation.^{18,19} In a phase 1 dose escalation study of Elotuzumab in 35 advanced myeloma patients, there was no maximum tolerated dose (MTD) identified up to 20 mg/kg (given every 14 days for 8 weeks).²⁰ Nine out of 34 patients (26.5%) had stable disease at day 56, suggesting limited single agent activity. At doses of 10 and 20 mg/kg of Elotuzumab, SLAMF7 receptors on bone marrow-derived myeloma cells were consistently saturated.²⁰ Mean terminal phase half-life

increased with a dose escalation ($T_{1/2}$ of 7.8 days with 20 mg/kg) suggesting a saturation of target-mediated elimination.²⁰ Transient decreases in lymphocyte counts were observed (within hours, in both CS1⁺ and CS1⁻ subsets) but returned to baseline levels by day 7.²⁰ Several phase II and III trials using combination therapy with Elotuzumab have been conducted in myeloma.²¹ Most recently, a phase 3 trial comparing Elotuzumab (10 mg/kg days 1, 8, 15, and 22 for first 2 cycles, then on days 1 and 15 with third cycle), lenalidomide and dexamethasone with lenalidomide plus dexamethasone in relapsed/refractory myeloma has been reported.¹ After a median follow-up of 24.5 months, median progression-free survival (PFS) was 19.4 months in Elotuzumab group vs. 14.9 months in control group ($P < 0.001$).¹ This very promising anti-CS1/SLAMF7 monoclonal antibody therapy with Elotuzumab has now been FDA approved and added to the armamentarium of anti-myeloma therapy. Overall, Elotuzumab appears to be well tolerated, with most common adverse events with single agent therapy being infusion-related reactions.²² In the phase 3 trial, Elotuzumab group had higher grade 3-4 lymphopenia (77% vs. 49%).¹ There was also a suggestion that grade 3 or 4 neutropenia incidence may be lower in Elotuzumab group (34% vs. 44%). Based on the prior clinical studies of Elotuzumab in relapse/refractory myeloma, Elotuzumab was demonstrated to be safe and effective for its treatment at a dose of 10 mg/kg in combination with lenalidomide.

As noted previously, it is critical that the Fc portion of Elotuzumab is able to bind to the Fc γ RIIIa receptor expressed on NK cells.^{8,9} The Fc γ RIIIa gene has allelic variation that determines the affinity of the Fc γ RIIIa receptor for IgG1 antibodies such as elotuzumab.⁹ In a phase 2 study of Elotuzumab plus bortezomib/dexamethasone for relapse/refractory multiple myeloma, Jakubowiak et al. evaluated the associations of Fc γ RIIIa receptor polymorphisms and clinical outcomes.²³ Patients who were homozygous for the high-affinity Fc γ RIIIa V (VV) allele had a longer PFS compared to those with homozygous for the low-affinity Fc γ RIIIa (FF) allele (22.3 months vs. 9.8 months),²³ suggesting the importance of evaluation of Fc γ RIIIa polymorphisms to predict better disease control in subsets of myeloma patients.

Study Rationale:

Disruption of interactions between myeloma cells and the microenvironment by targeting SLAMF7 using Elotuzumab (anti-CS1/SLAMF7 monoclonal antibody) could potentially abrogate drug-resistance and sensitize cells that are losing response to lenalidomide. Elotuzumab could potentially increase the NK cell activity in the context of lenalidomide therapy. We hypothesize that addition of Elotuzumab to myeloma patients who demonstrate serologic relapse/progression to single agent lenalidomide maintenance may modulate anti-myeloma immune response and render those patients into better response and prolong time to progression.

1.3 Overview of Elotuzumab

Elotuzumab (EMPLICITI™, Bristol-Myers Squibb Company [BMS], New York, NY, USA) is a fully humanized recombinant monoclonal immunoglobulin G1 (IgG1) antibody that binds human SLAMF7 (also CS1, CRACC). The unique epitope of Elotuzumab is located within the membrane proximal C2 domain of SLAMF7. The cell surface glycoprotein SLAMF7 is universally and highly expressed on patient MM cells, irrespective of cytogenetic abnormalities and the degree of disease progression. The exact role of SLAMF7 in myeloma cells is still unknown. Stable knockdown of SLAMF7 in MM cells resulted in decreased cell growth and colony formation in vitro,²⁵ as well as reduced tumor burden and increased survival of animals in a xenograft mouse model.²⁶ Homing of myeloma cells to the bone marrow, adhesion, and survival within the bone marrow microenvironment were impacted, indicating an involvement of SLAMF7 in the pathogenesis of MM. Elotuzumab has been evaluated for the treatment of MM in a series of clinical trials. The first-in-human study (Study 1701) assessed safety and tolerability as well as PK of Elotuzumab as a single agent. However, the antitumor effects of Elotuzumab were largely determined in combination with established myeloma therapies. In Study 1701, the safety and tolerability as well

as PK and pharmacodynamics of different doses of Elotuzumab (dose cohorts from 0.5 to 20 mg/kg body weight) were analyzed in 35 patients with RRMM. Saturation of SLAMF7 receptors was observed at Elotuzumab doses of 10–20 mg/kg. Despite plasma cell target saturation, no objective myeloma responses were observed.²⁰ Based on the European Society of Blood and Marrow Transplantation myeloma response criteria, 25 patients (73.5%) had progressive disease and nine patients (26.5%) were classified as having stable disease, demonstrating minimal single-agent activity of Elotuzumab. These findings substantiate the challenge to effectively activate and direct cells of the immune system to kill myeloma cells in patients with compromised immune function, in particular, with compromised NK cell function. In Study 1701, patients were heavily pretreated and had received a median of 4.5 prior therapies including lenalidomide, thalidomide, and/or bortezomib. To further evaluate the association between NK cell status and the efficacy of Elotuzumab monotherapy, a Phase II biomarker study (Study CA204011) is currently ongoing in patients with high-risk smoldering MM.

1.3.1 Combination studies of Lenalidomide and Elotuzumab

Lenalidomide is an oral IMiD that has been shown to directly kill MM cells, stimulate T cells to produce IL-2, increase NK cell proliferation, and lower the threshold required for NK cell activation.^{27,28} Based on data of several Phase III trials, lenalidomide in combination with low-dose dexamethasone (L/d) was approved for treatment of newly diagnosed MM patients ineligible for stem cell transplantation²⁹ and of patients with relapsed MM who have received at least one prior therapy.^{30,31} A meta-analysis of randomized controlled trials confirmed the survival advantage of treatment with L/d compared with other first-line therapies in patients with previously untreated MM.³²

The triple combination therapy of Elotuzumab, lenalidomide, and dexamethasone (E–L/d) was evaluated in a Phase I/II dose escalation study (Study 1703) and two large Phase III studies (ELOQUENT-1 and -2) in patients with newly diagnosed MM and RRMM, respectively. While ELOQUENT-1 is still ongoing with first results to be expected in 2017, data of ELOQUENT-2 are already available showing substantial evidence of effectiveness for E–L/d in the treatment of patients with RRMM who have received one to three prior therapies.

In this study, a total of 646 patients were enrolled (321 in the E–L/d arm and 325 in the L/d arm). Efficacy results of 635 treated patients showed a significant increase in tumor response of 78.5% versus 65.5% and median progression-free survival (mPFS) of 19.4 versus 14.9 months of E–L/d over L/d, respectively.³³ Based on data of a 3-year follow-up analysis, the progression-free survival (PFS) benefit of patients on E–L/d was maintained during this period. Exploratory analysis revealed a median delay of 1 year in the time to next treatment in patients treated with E–L/d compared with L/d-treated patients (33 months on E–L/d vs 21 months on L/d). Preliminary analysis of overall survival (OS) also indicated an advantage for patients treated with E–L/d.³⁴ Of note, the benefit in PFS and OS of patients on E–L/d was observed for all patient subgroups independent of age, disease stage, response to most recent line of therapy, number and nature of prior therapies, as well as high-risk cytogenetic profile.^{33,34}

Based on the Phase III efficacy data and the observed adverse events (AEs) (see “Safety of Elotuzumab treatment”), both the FDA and the EMA approved Elotuzumab in combination with lenalidomide at 25 mg days 121 and dexamethasone for the treatment of patients with RRMM.

Safety and tolerability data showed that minimal incremental toxicity was associated with addition of Elotuzumab to L/d. Significant differences in grade 3/4 AEs were observed for lymphopenia (78% on E–L/d vs 49% on L/d) and neutropenia (35% on E–L/d vs 44% on L/d). The rates for other grade 3/4 AEs including anemia, thrombocytopenia, cardiac or renal disorders were similar between the treatment groups. Infections (any grade) were reported in 83% of patients in the Elotuzumab group versus 75% in the control group. After adjustment for drug exposure, infection rates were equal in the two groups (196 and 193 events per 100 patient-years on E–L/d and L/d, respectively).³⁵

The incidence of herpes zoster infections was 4.1 versus 2.2 per 100 patient-years, respectively. Despite the finding of increased lymphopenia which may reflect alterations in lymphocyte trafficking, there was no evidence of

increased autoimmunity or other sequelae of immune dysregulation.³³ This confirmed previous results in whole blood samples from healthy individuals tested for the effects of Elotuzumab on the numbers of T, NK, and B cells. Elotuzumab treatment did not result in substantial depletion of major lymphocyte subsets.³⁶

Infusion reactions (mostly grade 1/2) occurred in only 11% of patients treated with E-L/d³⁵ and usually presented as pyrexia, chills, headache, flushing, and/or hypertension. Most infusion reactions were observed during the first dose of Elotuzumab. They were usually mild to moderate and resolved spontaneously within 24 hours or after management as clinically indicated. No patient experienced grade 4–5 reactions, and all but two patients could continue Elotuzumab treatment.³³

Furthermore, second primary malignancies were observed in 7% of patients on E-L/d compared with 4% on L/d. However, after adjustment for exposure to study therapy, the incidence rates were similar at 3.5 and 2.8 second primary cancers per 100 patient-years, respectively.³³

In Study CA204-112 ([NCT02159365](#)), treatment of Elotuzumab administered over ~1 hour in combination with L/d was evaluated in 70 patients with newly diagnosed or relapsed/refractory MM.^{37,38} All patients were required to have a premedication regimen before each dose of Elotuzumab. The infusion rate was accelerated from 0.5 to 5 mL/min at the start of the third dose in treatment cycle 1. At data cutoff, infusion reactions were observed in only two patients. The reactions were of grade 1/2 intensity and both patients continued treatment with Elotuzumab. No grade 3/4 infusion reactions had occurred by the end of treatment cycle 2. The administration of Elotuzumab at a faster rate may provide a safe option to reduce treatment time for patients.

2 Study objectives

2.1 Primary Objective

- Progression free survival with Elotuzumab plus lenalidomide when Elotuzumab is added to multiple myeloma patients with serologic relapse/progression while receiving lenalidomide maintenance for each cohort

2.2 Secondary Objectives

- Overall response rate (ORR) with Elotuzumab and lenalidomide for each cohort
- Minimum response (MR) or better rate with Elotuzumab and lenalidomide for each cohort
- Time to next treatment (TTNT) for each cohort
- Comparison of clinical outcomes (cohort A versus B)
- Fcγ RIIIA receptor polymorphisms (homozygous for high-affinity V (VV) allele vs. low affinity F (FF) allele)
- Effect of Elotuzumab added to lenalidomide on phenotypic characteristics of the immune infiltrate and correlation with therapeutic efficacy

3 Overall study design

Randomized parallel 2-cohort phase 2 study of Elotuzumab given at 10 mg/kg weekly during induction in combination with lenalidomide (either 25 mg or 10 mg) in patients with multiple myeloma who progress or relapse serologically while on single agent lenalidomide maintenance. Patients will be randomized to either (1) cohort A = lenalidomide 25 mg PO daily days 1-21 or (2) cohort B = lenalidomide 10 mg PO daily days 1-21 with Elotuzumab. We selected the dose of Elotuzumab at 10 mg/kg weekly dosing followed by monthly infusion of 20 mg/kg based on the safety and tolerability profile in the published phase 3 study and other studies of combination therapy with

bortezomib,¹⁻³ as well as an ongoing study in combination with pomalidomide (NCT02612779). Elotuzumab will be administered intravenously on days 1, 8, 15, and 22 during the first 2 cycles, then on day 1 of each cycle starting third cycle. The combination therapy with Elotuzumab and lenalidomide will be continued until further progression of myeloma (based on response criteria) or intolerance.

A total of 60 eligible patients will be randomized into one of two study arms in 1:1 ratio. Stratification factors are risk (standard vs. high) and lenalidomide maintenance post-transplant (yes vs. no). A permuted-block randomization will be applied to ensure a balanced assignment to each treatment arm. Randomization will be accomplished using the Moffitt Cancer Center web-based Subject Registration and Randomization System (SRAR). The SRAR program is accessed using an individual secure identification key that authenticates the user into the Moffitt network.

[figure not shown]
Combination dosing schedule:

(1) Cohort A:

- Elotuzumab 10 mg/kg IV weekly (days 1, 8, 15 and 22) for 2 cycles, then 20 mg/kg every 4 weeks
- Lenalidomide 25 mg PO daily days 1-21 out of a 28-day schedule

(2) Cohort B:

- Elotuzumab 10 mg/kg IV weekly (days 1, 8, 15 and 22) for 2 cycles, then 20 mg/kg every 4 weeks
- Lenalidomide 10 mg PO daily days 1-21 out of a 28-day schedule

Response assessment:

The Consensus on Uniform Reporting of Response will be used to evaluate response.⁴ Myeloma patients enrolled in this clinical study will be assessed for disease response after every cycle. Time to disease progression will be defined as the time from the day first Elotuzumab treatment to the time of myeloma progression.

4 Study population

Patients with multiple myeloma who demonstrate evidence of serologic relapse/progression while on lenalidomide maintenance given as part of **first** line therapy (including upfront high-dose chemotherapy followed by autologous hematopoietic cell transplantation (HCT)) without symptomatic relapse/progression. Lenalidomide maintenance is defined as **single agent** lenalidomide therapy of any doses up to 15 mg PO daily for up to 28 days (28-day cycle). Relapse/progression is defined as increase of 25% from the lowest response value (for either serum or urine M-spikes), absolute increase in serum M-spike ≥ 0.5 g/dL, absolute increase in urine M-spike ≥ 200 mg/24hour, or the difference between involved and uninvolved free light chain (FLC) levels of absolute increase with > 10 mg/dl (only for those without measurable serum and urine M-spikes) There will be 30 subjects in each cohort for total accrual of 60 subjects.

Patients must have baseline evaluations performed prior to the first dose of study drug and must meet all inclusion and exclusion criteria. Results of all baseline evaluations, which assure that all inclusion and exclusion criteria have been satisfied, must be reviewed by the Principal Investigator or Co-investigators prior to enrollment of that patient. In addition, the patient must be thoroughly informed about all aspects of the study, including the study visit schedule and required evaluations and all regulatory requirements for informed consent. The written informed consent must be obtained from the patient prior to enrollment. The following criteria apply to all patients enrolled onto the study unless otherwise specified.

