4.1 Inclusion criteria

1. Patients with multiple myeloma who demonstrate evidence of serologic relapse/progression while on lenalidomide maintenance given as part of **first** line therapy (including upfront high-dose chemotherapy followed by autologous hematopoietic cell transplantation (HCT)) without symptomatic relapse/progression.

Lenalidomide maintenance is defined as **single agent** lenalidomide therapy of any doses up to 15 mg PO daily for 14-28 days (28-day cycle). Relapse/progression is defined as increase of 25% from lowest confirmed response value in one or more of the following criteria: Serum M –protein (absolute increase must be ≥ 0.5 g/dl)

Serum M-protein increase >1 g/dl, if the lowest M component was >5 g/dl

Urine M –protein (absolute increase must be > 200 mg in 24 hours)

In patients without measurable serum and urine M-protein levels, the difference between involved and uninvolved FLC levels (absolute increase must be > 10 mg/dl)

For patients relapsing from complete remission, relapse is defined as:

Reappearance of serum or serum M-protein by immunofixation or electrophoresis.

2. Male or female patients aged ≥ 18 years old

3. Ability to provide written informed consent obtained prior to participation in the study and any related procedures being performed

4. Measurable disease with at least 1 of the following assessed within 28 days prior to Cycle 1 Day 1:

A. Serum M-protein ≥ 0.5 g/dL,

B. Urine M-protein ≥ 200 mg/24 hour,

C. In subjects without measurable serum or urine M-protein, serum free light chain (SFLC) > 10 mg/dL (involved light chain) and an abnormal serum kappa lambda ratio

5. Patients must meet the following laboratory criteria within 28 days prior to Cycle 1, day 1:

- Absolute neutrophil count (ANC) $\geq 1 \times 10^9/L$
- Hemoglobin $\geq 10 \text{ g/dL}$
- Platelet count $\geq 75,000/\text{mm}^3$
- AST and ALT $\leq 2.5 \times \text{ULN}$
- Serum bilirubin $\leq 1.5 \times \text{ULN}$
- Serum Creatinine clearance $\geq 50\text{ml}/\text{min}$

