5.11 Treatment compliance

Records of study medication used, dosages administered, and intervals between visits will be recorded during the study.

6 Visit schedule and assessments**6.1 Visit schedule****Table 6-1****Evaluation and visit schedule**

Assessment	Screening 0-28 days	Day 1 Cycles 1- 2	Day 8	Day 15	Day 22	Day 1 Cycle 3 - beyond	End of Study
Assessment	Screening 0-28 days	Day 1 Cycle 1&2 +/- 3 days	Day 8	Day 15	Day 22	Day 1 C3- beyond +/- 3 days	End Of Study
Informed Consent	X						
Inclusion/exclusion criteria	X						
Vital signs, Physical examination and ECOG Performance Score ⁶	X	X				X	X
Concomitant medications ⁶	X	X				X	X
CBC + diff ⁶	X	X	X	X	X	X	X
CMP ⁶ ,Pregnancy Test ⁶	X	X	X	X	X	X	X
SPEP/UPEP ⁸ /immunofixation	X	X				X	X
Serum free light chains	X	X				X	X
Quantitative immunoglobulins	X	X				X	X
Skeletal survey ³	X					X ³	X ³
Bone marrow asp and bx with Cytogenetics, MM Fish Panel Lab correlative studies ¹		X ¹	X ¹				X ¹
MRD Testing	X ²						
Response Assessment	n/a						X
Study Drug Diaries	n/a	X				X ⁵	

Adverse Events ⁷	n/a	X	X	X		X	X
-----------------------------	-----	---	---	---	--	---	---

1. Bone marrow aspirate and biopsy will be done at screening and on cycle 2 day 1, and to confirm CR after 4 cycles, 8 cycles and as indicated and at time of PD for lab correlative studies as outlined in page 26. In parallel a peripheral blood sample will be collected for lab correlative studies at same time points and on day 1 of each cycle. Bone marrow aspirates (30mL volume) for correlative studies will be collected at baseline, Cycle 2 day 1, and thereafter for confirmation of CR, and at time of disease progression to analyze marrow-infiltrating immune populations by MPFC. In parallel, PBMCs, isolated from 20-30mL freshly drawn sample, will be analyzed similarly at 4-week intervals corresponding to Day 1 of each cycle as well as at time of progression.
2. MRD testing will be performed at screening, by flow cytometry and NSG on patients and as indicated on patients in hematologic complete remission. An aliquot of serum will be stored for those patients with IgG MM who achieved VGPR to evaluate extent of interference by the antibody therapy.
3. Bone survey will be done at screening and once yearly or when clinically indicated. May be substituted by PET scan or MRI as clinically indicated
4. Response assessment will be done every 2 cycles.
5. Study drug diaries will be collected after each cycle

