We have developed an approach to define these immunologic populations in much greater detail using MPFC. Leukocytes will be isolated from bone marrow aspirates by Ficoll-Hypaque gradient centrifugation after prior extraction of MM cells by CD138 positive magnetic bead selection. In parallel, leukocytes will be isolated in similar fashion from peripheral blood samples from each patient. After adequate viability is determined (>85% viable by trypan blue exclusion), leukocyte cell fractions from each patient sample, will be prepared according to three defined analysis panels (see **Table 1**) to characterize (a) maturation state, (b) subset composition (e.g. T_H1, T_H2, T_H17, T_{REG}, and CD8 $^{+}$ counterpart exhaustion status. In addition, lymphocyte stimulatory capacity and effector cytokine production (i.e. IFN- γ TNF- α and

Granzyme B) will be assessed as a benchmark of immune function. In brief, CD3⁺ T cells will be isolated from the leukocyte fraction of each sample by magnetic bead selection

(Miltenyi Biotech) to achieve approximately

Table 2. Myeloid Characterization by MPFC.

Myeloid Panel	
CD11b	CD38
CD13	CD71
CD14	CD45
CD15	CD64
CD16	CD80
CD33	CD163
CD34	CD124
CD117	Statistical Methods
HLA-DR	

7

99% of final cell stain and the preparation for MPFC analysis. Comparative analysis of disease in the cell myeloid compartment will be monitored using a 14-parameter panel designed to detect dendritic cell, myeloid suppressor cell, and macrophage populations, as detailed in Table 2. Immunophenotypic profiles will be discerned from sequential analysis of the individual patient samples at defined intervals. Bone marrow aspirates (30mL volume) will be collected at baseline, Cycle 2 day 1, and thereafter for confirmation of CR, and at time of disease progression to analyze marrow-infiltrating immune populations by MPFC. In parallel, PBMCs, isolated from 20-30mL freshly drawn sample, will be analyzed similarly at 4-week intervals corresponding to Day 1 of each cycle as well as at time of progression.

Phase II study

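### The immune-infiltrate objective credits elotuzumab with a before-after change that also contains a change in lenalidomide and the start of dexamethasone

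*Combined protocol and SAP*

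**What the plan says.** The objective in Section 2.2, repeated in 7.2, is the "Effect of Elotuzumab added to lenalidomide on phenotypic characteristics of the immune infiltrate and correlation with therapeutic efficacy". Section 6.5 places the interest in elotuzumab itself: it looks for immune features that predict that drug's efficacy and that could guide its timing and sequencing with partner drugs.

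- **Entry treatment.** Section 4.1 admits patients on single-agent "lenalidomide therapy of any doses up to 15 mg PO daily for 14-28 days (28-day cycle"). Section 4 (Study population) words the schedule differently, as "any doses up to 15 mg PO daily for up to 28 days (28-day cycle"), with no lower limit on days.
- **Study treatment.** The dosing schedule in Section 3 gives cohort A "Lenalidomide 25 mg PO daily days 1-21 out of a 28-day schedule" and cohort B "Lenalidomide 10 mg PO daily days 1-21 out of a 28-day schedule", both with elotuzumab.
- **Samples.** Section 6.5 states: "Bone marrow aspirates (30mL volume) will be collected at baseline, Cycle 2 day 1, and thereafter for confirmation of CR", and again at progression. Footnote 1 to Table 6-1 repeats this. Blood is analysed on day 1 of each cycle and at progression. Profiles are to be read from each patient's successive samples.
- **Premedication.** Sections 5.3, 5.4 and 5.10.1.1 require dexamethasone 28 mg orally and 8 mg intravenously before each elotuzumab infusion.
- **Analysis.** Section 7.2 gives methods for time-to-event and binary endpoints. It names no model for change in immune phenotype and no adjustment for lenalidomide exposure.

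**The concern.** A before-after comparison isolates an added drug only if everything else is held constant. Here the background drug changes when the new one starts, and the protocol itself says that the background drug acts on the cells being measured. Section 1.3.1 states that lenalidomide has been shown to "stimulate T cells to produce IL-2, increase NK cell proliferation, and lower the threshold required for NK cell activation", and Section 6.5 cites reversal of a T-cell dysfunction pattern in blood on exposure to it. The flow panels measure T and NK subsets, exhaustion markers and stimulation capacity.

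If the plan is followed as written, a shift produced by raising, lowering or pausing lenalidomide, or by dexamethasone, would be reported as an effect of elotuzumab. Because the lenalidomide change differs between cohorts and between patients, pooling them would also blur any shift it causes. Section 6.5 intends the results to inform later decisions on how to deliver elotuzumab, so the attribution matters beyond this trial.

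**Working it through.** The plan gives no figure for this objective, so there is none to reproduce. The check uses the plan's own doses and days.

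**1. Scheduled lenalidomide before and on study.** Exposure per 28-day cycle = daily dose × days taken. On study, cohort A is 25 × 21 = 525 mg and cohort B is 10 × 21 = 210 mg, each with 28 − 21 = 7 days off before the next day 1. The 5 mg row is an assumed low example, because the plan sets no minimum dose.

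| Maintenance at entry | mg per cycle | Scheduled days off | Daily dose change, A | Cycle ratio, A | Daily dose change, B | Cycle ratio, B |
|---|---|---|---|---|---|---|
| 15 mg × 28 d | 420 | 0 | +10 | 525/420 = 1.25 | −5 | 210/420 = 0.50 |
| 10 mg × 28 d | 280 | 0 | +15 | 525/280 = 1.88 | 0 | 210/280 = 0.75 |
| 10 mg × 21 d | 210 | 7 | +15 | 525/210 = 2.50 | 0 | 210/210 = 1.00 |
| 15 mg × 14 d | 210 | 14 | +10 | 525/210 = 2.50 | −5 | 210/210 = 1.00 |
| 5 mg × 14 d (assumed) | 70 | 14 | +20 | 525/70 = 7.50 | +5 | 210/70 = 3.00 |

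In cohort A the scheduled daily dose rises for everyone, by at least 25 − 15 = 10 mg. In cohort B it can go either way or not move. Of the schedules shown, only 10 mg for 21 days leaves both daily dose and cycle total unchanged in B.

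**2. Timing of the samples.** Cycle 2 day 1 follows lenalidomide-free days 22 to 28. The baseline marrow may fall anywhere in the 0-28 day screening window. Nothing ties it to a day of the maintenance cycle or fixes the gap between maintenance and cycle 1 day 1. Days since the last capsule are therefore scheduled at the second sample and uncontrolled at the first.

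**3. Dexamethasone.** Entry treatment is single-agent lenalidomide. On study, each infusion brings 28 + 8 = 36 mg of dexamethasone. Four infusions in cycle 1 (days 1, 8, 15 and 22) give 4 × 36 = 144 mg nominal before the cycle 2 day 1 sample.

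**4. What can be estimated.** Write a patient's change from baseline as

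change = E + D + β × (change in lenalidomide) + error,

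where E is the elotuzumab effect and D the dexamethasone effect. Both drugs start in all 60 patients, so E and D multiply identical columns of ones. A rank check on the three-column design (elotuzumab, dexamethasone, lenalidomide change) gives rank 2. Only the sum E + D can be estimated, and only after the lenalidomide term has been modelled correctly.

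In the difference A minus B, E and D cancel under this additive model. What remains is the randomised lenalidomide contrast: 25 − 10 = 15 mg daily, or 525 − 210 = 315 mg per cycle. That contrast is a valid estimate of the lenalidomide-dose effect given elotuzumab and dexamethasone. It carries no information on the effect of elotuzumab.

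**The case against.** The strongest reply is that the wording, elotuzumab added to lenalidomide, echoes the primary objective and can be read as the effect of the combination. On that reading nothing is misattributed and only clarity is at issue. This has some force, but Section 6.5 speaks of the efficacy and delivery of elotuzumab specifically, so the narrower attribution is a natural reading and should be closed off.

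Three further points stand. First, the objective also covers correlation with efficacy. The Cox, Fine-Gray and logistic models in 7.2 can serve that part, and the criticism does not reach it in the same way. Second, much of the needed information is already gathered: Section 5.10 asks for medications within 30 days of screening, screening includes prior therapy, and Section 5.11 and the diaries cover on-study dosing. What is missing is the link to sample dates. CRF capture is also in doubt, since a footnote to Table 6-1 limits the concomitant-medication row to items related to adverse events. Third, this is a secondary, correlative aim that touches neither PFS nor the sample size.

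A reader might infer more than the documents support:

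- **That the trial can separate the drugs**, through the A-versus-B contrast, a lenalidomide covariate or the cohort B patients whose lenalidomide is unchanged. It cannot, because dexamethasone starts with elotuzumab in all of them.
- **That every cohort A patient has actually taken a higher dose by the second sample.** Only the scheduled dose is certain to rise; Section 5.8 allows reductions and holds.
- **That days off drug are shown to change.** They are uncontrolled at baseline, which is a different statement.
- **That a probability of a false finding can be given.** The documents state no size of immune shift, no test and no number of evaluable pairs.

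**Conclusion.** The point holds in this form: the planned before-after change mixes elotuzumab, a change in lenalidomide exposure and newly started dexamethasone, and cannot be credited to elotuzumab alone. Scheduled lenalidomide per cycle in cohort A rises to 1.25 times the highest permitted entry exposure, and by more from any lower one. In cohort B the ratio runs from 0.50 upwards, reaching 3.00 if 5 mg for 14 days is taken as the low example. From continuous 10 mg the two cohorts move in opposite directions, +88% and −25%.

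These figures assume treatment as scheduled. That lenalidomide affects the measured cells is the protocol's own statement. For dexamethasone the aliasing is structural; the documents do not say how large its effect on the panels would be. The size of the resulting bias is unknown. The change is worth making because it is cheap and alters what may be concluded, but it leaves the primary analysis untouched.

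**What to change.** In Sections 2.2, 6.5 and 7.2:

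1. State the objective and its conclusions as the change in immune phenotype under the combination regimen, including dexamethasone premedication, and not as an effect of elotuzumab.
2. Report immune change separately by cohort. Use the randomised A-versus-B difference in change, adjusted for the baseline value, to estimate the effect of 25 versus 10 mg lenalidomide.
3. Link maintenance dose and schedule, and days since the last lenalidomide dose, to each correlative sample, using the medication history and diaries already collected, and make sure that these items reach the CRF. Use change in lenalidomide exposure as a covariate only in a sensitivity analysis, since entry dose is not randomised.
4. If cohort B patients with unchanged lenalidomide are shown, label them as a small, descriptive subset in which elotuzumab is still confounded with dexamethasone.

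Sections 4 and 4.1 should also be reconciled on the number of maintenance days, because that defines baseline exposure.

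The cost is a narrower claim, small numbers in the subset and minor CRF work. No treatment, sample or assay changes.
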